6.2 Dose modifications

6.2.1 Dose modification and dose delay

6.2.1.1 Hepatic impairment dose modifications

Hormone receptor-positive advanced breast cancer, advanced neuroendocrine tumors of gastrointestinal, lung, or pancreatic origin, and advanced renal cell carcinoma:

Severe hepatic impairment (Child-Pugh C) – not recommended. TSC with SEGA

Patients \geq 18 years of age:

- Severe hepatic impairment (Child-Pugh C) – not recommended.

Everolimus whole blood trough concentrations should be assessed approximately 2 weeks after commencing treatment or after any change in hepatic (Child-Pugh) status.

Patients $<$ 18 years of age:

Afinitor is not recommended for patients $<$ 18 years of age with TSC who have SEGA and hepatic impairment.

Afinitor is not recommended for patients with hepatic impairment who require doses below 2 mg every other day or 2.5 every other day. Everolimus exposure was increased in patients with mild (Child-Pugh A), moderate (Child-Pugh B), and severe (Child-Pugh C) hepatic impairment (see Section 5.2.3). Everolimus is not recommended for use in postmenopausal women with hormone receptor positive advanced breast cancer, or in patients with advanced neuroendocrine tumors of gastrointestinal, lung, or pancreatic origin or advanced renal cell carcinoma with severe hepatic impairment (Child-Pugh C) unless the potential benefit outweighs the risk.

Special Populations

Geriatrics (≥ 65 years) :

No dosage adjustment is required.

Renal impairment :

No dosage adjustment is required.

Ethnicity :

Pharmacokinetic characteristics are similar for Caucasian and Japanese subjects.

Pharmacokinetic studies in Black transplant patients have shown an average 20% higher clearance.

6.2.1.2 Dosing modifications

For patients who do not tolerate the protocol-specified dosing schedule, dose adjustments are not permitted.

Table 6-1 and Table 6-2 list the dosing guidelines for Everolimus-related non-hematologic and hematologic toxicities.

Management of severe or intolerable adverse drug reactions (ADRs) may require temporary dose interruption of Afinitor therapy.

The proceeding sections summarize recommendations for dose interruption, or discontinuation of Afinitor in the management of ADRs. General management recommendations are also provided as applicable. Clinical judgment of the treating physician should guide the management plan of each patient based on individual benefit/risk assessment.

Table 6-1 Dosing guidelines for Everolimus-related non-hematologic toxicities

Toxicity	Action
Non-Infectious Pneumonitis	Discontinue Everolimus.
Reactivation of HBV or HCV flare	Discontinue Everolimus.
AST or ALT elevation Grade 1 ($>$ ULN - 3.0 x ULN)	Maintain current dose level
Grade 2 ($>$ 3.0 - 5.0 x ULN)	
AST or ALT elevation Grade 3 ($>$ 5.0 - 20.0 ULN)*	Discontinue Everolimus
AST or ALT elevation Grade 4 ($>$ 20 x ULN)*	Discontinue Everolimus
Intolerable grade 2 mucositis, or grade 3 AE, except hyperglycemia or hypertriglyceridemia or hypercholesterolemia (see Section 6.2.3.8)	Discontinue Everolimus
Any other grade 4	Discontinue Everolimus
Grade 3 or 4 clinical liver failure (asterixis or encephalopathy/coma)	Discontinue Everolimus

* Should HCV flare be confirmed, the guidelines for flare must take precedence (Table 6-6)

Table 6-2 Dosing guidelines for Everolimus-related hematologic toxicities

Toxicity	Action
Grade 2 thrombocytopenia (platelets $<$ 75, \geq 50 x10 ⁹ /L)	No action
Grade 3 thrombocytopenia (platelets $<$ 50, \geq 25 x10 ⁹ /L)	Discontinue Everolimus
Grade 4 thrombocytopenia (platelets $<$ 25 x10 ⁹ /L)	Discontinue Everolimus
Grade 3 neutropenia or anemia (neutrophil $<$ 1, \geq 0.5 x10 ⁹ /L)	Discontinue Everolimus
Grade 4 neutropenia or anemia	Discontinue Everolimus
Febrile neutropenia	Discontinue Everolimus

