6.2.2.9 Management of non-infectious pneumonitis

Non-infectious pneumonitis is a class effect of rapamycin derivatives. Cases of non-infectious pneumonitis (including interstitial lung disease) have also been described in patients taking Everolimus. Some of these have been severe and on rare occasions, a fatal outcome was observed.

- A diagnosis of non-infectious pneumonitis should be considered in patients presenting with non-specific respiratory signs and symptoms such as hypoxia, pleural effusion, cough or dyspnea, and in whom infectious, neoplastic and other non-medicinal causes have been excluded by means of appropriate investigations. Opportunistic infections such as PJP should be ruled out in the differential diagnosis of non-infectious pneumonitis. Patients should be advised to report promptly any new or worsening respiratory symptoms.

Patients who develop radiological changes suggestive of non-infectious pneumonitis and have few or no symptoms may continue Afinitor therapy without dose alteration.

If symptoms are moderate (grade 2), consideration should be given to interruption of therapy until symptoms improve. The use of corticosteroids may be indicated. Afinitor may be reintroduced at a daily dose approximately 50% lower than the dose previously administered.

For cases of grade 3 non-infectious pneumonitis, discontinue Afinitor. For cases of grade 4 non-infectious pneumonitis, Afinitor therapy should be discontinued. Corticosteroids may be indicated until clinical symptoms resolve.

For patients who require use of corticosteroids for treatment of non-infectious pneumonitis, prophylaxis for pneumocystis jirovecii pneumonia (PJP) may be considered. The two compounds studied most extensively for prophylaxis against PJP have been trimethoprim-sulfamethoxazole, given orally, and pentamidine, given as an aerosol.

If non-infectious pneumonitis develops, the guidelines in Table 6-3 should be followed. Consultation with a pulmonologist is recommended for any case of pneumonitis that develops during the study.

Table 6-3 Management of non-infectious pneumonitis

Worst grade pneumonitis	Suggested investigations	Management of pneumonitis	Everolimus dose adjustment
Grade 1 (Asymptomatic, radiographic findings only)	CT scans with lung windows.	No specific therapy is required	No dose adjustment required. Initiate appropriate monitoring.

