Grade 2 (Symptomatic, not interfering with Activities of Daily Living)	CT scan with lung windows. Consider pulmonary function testing includes: spirometry, DLCO, and room air O ₂ saturation at rest. Consider a bronchoscopy with biopsy and/or BAL. Monitoring at each visit until return to ≤ grade 1. Return to initial monitoring frequency if no recurrence.	Symptomatic only. Consider corticosteroids and/or other supportive therapy if symptoms are troublesome.	Rule out infection and consider interruption of Everolimus until symptoms improve to Grade ≤ 1.
Grade 3 (Symptomatic, Interfering with Activities of Daily Living. O ₂ indicated)	CT scan with lung windows and pulmonary function testing includes: spirometry, DLCO, and room air O ₂ saturation at rest. Monitoring at each visit until return to ≤ grade 1. Return to initial monitoring frequency if no recurrence. Bronchoscopy with biopsy and/or BAL is recommended.	Consider corticosteroids if infective origin is ruled out. Taper as medically indicated.	Rule out infection and discontinue Everolimus until symptoms improve to Grade ≤ 1.
Grade 4 (Life-threatening, ventilator support indicated)	CT scan with lung windows and required pulmonary function testing, if possible, includes: spirometry, DLCO, and room air O ₂ saturation at rest. Monitoring at each visit until return to ≤ grade 1. Return to initial monitoring frequency if no recurrence. Bronchoscopy with biopsy and/or BAL is recommended if possible.	Consider corticosteroids if infective origin is ruled out. Taper as medically indicated.	Rule out infection and discontinue Everolimus.

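### The protocol's dose rules contradict each other on pneumonitis, on whether a reduced dose is ever allowed, and on the dose of patients treated after the sixth

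*Protocol*

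**What the plan says.** **Reduced dose.** Section 6.2.1.2 says "For patients who do not tolerate the protocol-specified dosing schedule, dose adjustments are not permitted". It allows temporary interruption and adds: "The proceeding sections summarize recommendations for dose interruption, or discontinuation of Afinitor in the management of ADRs". Section 6.2.2.9 then says, for grade 2 pneumonitis: "Afinitor may be reintroduced at a daily dose approximately 50% lower than the dose previously administered".

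**Pneumonitis.** In Table 6-1 the row "Non-Infectious Pneumonitis" has the single action of discontinuing, with no grade stated. The text of 6.2.2.9 says: "Patients who develop radiological changes suggestive of non-infectious pneumonitis and have few or no symptoms may continue Afinitor therapy without dose alteration". It also says: "For cases of grade 3 non-infectious pneumonitis, discontinue Afinitor". It hands over to another table: "If non-infectious pneumonitis develops, the guidelines in Table 6-3 should be followed". At grade 2 that table says "Rule out infection and consider interruption of Everolimus until symptoms improve to Grade" 1 or lower; at grade 3 it says to discontinue until the same improvement.

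**Dose of later patients.** The mucositis paragraph of Section 4.1 triggers a 50% reduction when mucositis worsens in two of the first six patients. It gives no grade, relatedness, cohort or reference dose. The DLT rule (Sections 4.1, 6.1 and 9.1) counts only everolimus-related events of grade 3 or higher and assigns only 5 mg or 10 mg. Section 11.4 refers the reader to Section 9.1 for a de-escalation procedure; 9.1 has none.

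**The concern.** The initial objective is to document which of two doses is safe. That requires one action for a given event and grade, and one dose for the next patient. As written, a physician reading Table 6-1 and another reading Table 6-3 would treat the same grade 1 or 2 pneumonitis differently. A site applying the mucositis rule and a site applying the DLT rule could treat the next patient at different doses. The protocol itself expects mucositis to be of little concern, but the two-of-six rule exists for the case where that expectation fails, and in that case it does not yield a single instruction. The planned analysis by 5 mg and 10 mg strata also has no place for a patient at another dose.

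**Working it through.** The conflict is textual, so the main check sets the passages side by side. The arithmetic only sizes it.

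**1. Pneumonitis, by grade**

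| Grade | Table 6-1 | 6.2.2.9 text | Table 6-3 |
|---|---|---|---|
| 1 | Discontinue | May continue (few or no symptoms) | No dose change |
| 2 | Discontinue | Consider interrupting; may restart about 50% lower | Consider interrupting until grade 1 or lower; no restart dose |
| 3 | Discontinue | Discontinue | Discontinue until grade 1 or lower |
| 4 | Discontinue | Discontinue | Discontinue |

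Tables 6-1 and 6-3 differ at grades 1, 2 and 3 and agree at grade 4. If Table 6-3 governs, as 6.2.2.9 says, the Table 6-1 row is wrong as written. Two questions stay open even then: the restart dose at grade 2, and whether a grade 3 stop is permanent.

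**2. Reduced dose.** Section 6.2.1.2 rules out dose adjustment for intolerance; 6.2.2.9 allows it. Giving Table 6-3 precedence does not settle this, because its grade 2 row names no restart dose.

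**3. Patients after the sixth.** The protocol's own totals reproduce: 3 + 10 = 13, 6 + 10 = 16, and 10.

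- *No DLT in the first three (13 patients).* The first six are three at 5 mg and three at 10 mg. Patients after the sixth: 13 − 6 = 7. The DLT rule gives them 10 mg. Half of 10 mg is 5 mg and half of 5 mg is 2.5 mg, so the reduction has no single base.
- *One DLT in three, then none in three (16 patients).* All six are at 5 mg. Patients after the sixth: 16 − 6 = 10. The DLT rule escalates them to 10 mg; the mucositis rule, if triggered, reduces. Again 5 mg or 2.5 mg can be read.
- *No escalation (10 patients).* Patients after the sixth: 10 − 6 = 4. The DLT rule keeps all ten at 5 mg; a halving would give these four 2.5 mg, which is not a planned level.

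Section 6.1 lists 2.5, 5 and 10 mg tablets, so supply does not settle the reading.

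**How often the 16-patient path arises.** With independent patients and per-patient DLT risk p (not given in the protocol):

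P = 3p(1 − p)² × (1 − p)³ = 3p(1 − p)⁵

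| p | 0.05 | 0.10 | 1/6 | 0.20 | 0.30 |
|---|---|---|---|---|---|
| P | 0.116 | 0.177 | 0.201 (maximum) | 0.197 | 0.151 |

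This is the chance of reaching the path, not of a clash, which also needs two of six patients with worsening mucositis.

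**How readily the mucositis rule fires.** With assumed worsening risk m per patient (also not in the protocol), P(at least 2 of 6) = 1 − (1 − m)⁶ − 6m(1 − m)⁵, which is 0.114 at m = 10%, 0.345 at 20%, 0.580 at 30% and 0.891 at 50%.

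**Precision.** Section 9.1's standard error of 0.32 standard deviations is right for ten patients: 1/√10 = 0.316. In the 10-patient path a reduction after the sixth would leave six at 5 mg, where the factor is 1/√6 = 0.408.

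**The case against.** Section 6.2.1.2 also says that the treating physician's clinical judgment should guide management, and it calls its tables guidelines. Section 6.2.2.9 uses permissive wording and names Table 6-3 as the one to follow, so a specific guide can be taken to override a general list. Grade 1 pneumonitis is a radiographic finding, Table 7-1 schedules no chest imaging, and no visit falls within the five dosing days if dosing starts when drug is dispensed (day 15, next visit day 22, each plus or minus one day). The mucositis rule can be read as an extra safeguard overlaying the DLT rule, with 50% meaning half of the dose then in use.

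Much of this stands as a limit on the pneumonitis and reduced-dose points: they matter mainly when symptoms are reported between visits. It does not remove them. Table 6-1 has a precedence note for hepatitis C flare but none for pneumonitis. Clinical judgment does not reconcile a prohibition on dose adjustment with a described half-dose restart. The grade 3 text also still differs from the table it endorses.

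The overlay reading of the mucositis rule is reasonable, but the protocol does not state it. Even under it, the rule collides with a cohort fixed at ten patients on 5 mg, and Section 9.1 still lacks the de-escalation that Section 11.4 cites.

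**Conclusion.** The concern holds. Tables 6-1 and 6-3 conflict at three of four pneumonitis grades, and two of those questions survive if Table 6-3 governs. The bar on dose adjustment conflicts with the half-dose restart. The mucositis and DLT rules leave the dose unsettled for 7 of 13, 10 of 16 or 4 of 10 patients once the mucositis trigger is met. The last item weighs most, because it sets the dose of later patients and does not depend on events being caught within the five-day course.

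Opposite orders, escalate and reduce, after six patients at 5 mg arise only in the 16-patient path, whose probability is at most 20.1% under independent patients with a common DLT risk. The protocol gives no risk of worsening mucositis, so no clash probability is claimed. The stated totals of 10, 13 and 16 and the 0.32 factor are correct as written.

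**What to change.** - Reconcile Table 6-1 with the text of 6.2.2.9 and with Table 6-3, so that each pneumonitis grade has one action.
- Reconcile 6.2.1.2 with the half-dose restart in 6.2.2.9.
- Reconcile the Section 4.1 mucositis rule with the DLT rule in 4.1, 6.1 and 9.1. State which patients and dose level it applies to, what the 50% refers to, and which rule prevails when both apply. Place it in 9.1, where 11.4 already points.
- Editorial: cross-reference the Table 6-1 row on intolerable grade 2 mucositis (discontinue) with 6.2.2.6 (interrupt and restart at grade 2), and correct the reference to Section 6.2.3.8, which does not exist.

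Which action or dose applies in each case is for the investigators and the company to decide. The cost is amendment wording and its review, with no added patients or procedures.

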Premature patient withdrawal	Point/time when the patient exits from the study prior to the planned completion of all study treatment administration and/or assessments; at this time all study treatment administration is discontinued and no further assessments are planned, unless the patient will be followed for progression and/or survival
Stop study participation	Point/time at which the patient came in for a final evaluation visit or when study treatment was discontinued whichever is later
Study treatment	
Includes any drug or combination of drugs in any study arm administered to the patient (subject) as part of the required study procedures, including placebo and active drug run-ins.
 
In specific examples, it is important to judge investigational treatment component relationship relative to a study treatment combination; study treatment in this case refers to the investigational and non-investigational treatments in combination.

Study treatment discontinuation	Point/time when patient permanently stops taking study treatment for any reason; may or may not also be the point/time of premature patient withdrawal
Supportive treatment	Refers to any treatment required by the exposure to a study treatment, e.g. premedication of vitamin supplementation and corticosteroid for pemetrexed disodium.
Variable	Identifier used in the data analysis; derived directly or indirectly from data collected using specified assessments at specified time points

Schema

Step 1¹

R
E
G
I
S
T
E
R

RT or chemoRT
administration

Step 2²

R
E
G
I
S
T
E
R

Everolimus
Administration³

↓↓↓↓

CORRELATIVE STUDIES⁴

¹ Patients with locally advanced squamous cell carcinoma of the Head and Neck treated with curative intent either in the post-operative or definitive setting with high dose radiotherapy (RT ≥ 50 Gy) with or without chemotherapy (chemoRT) will be eligible

² Verify eligibility for everolimus treatment. Patients with clinically severe gland dysfunction (i.e., those with loss of at least 50% of the pre-radiotherapy value) will be eligible for everolimus treatment.

³ Everolimus (5 or 10 mg) po qd, x 5days only, starting 2 weeks after definitive treatment completion

⁴ Saliva flow rates and xerostomia surveys will be obtained at baseline, after 3 and 6 weeks of RT/chemoRT, prior to everolimus administration, at completion of the 5 day everolimus course and at 1,3 and 6 months after RT/chemoRT completion

1 Background

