- 9) If the patient is too dry, (dry mouth), it is possible to add the weight of the gum base to the pre-weight measure with the gum base in the cup of saliva.

Analysis of saliva: The collection tubes are weighed before and after saliva collection. The difference equates to the total mL collected which is divided by the number of minutes of collection. Saliva is stored at -80°C for further analysis on salivary protein composition at a later date (described in correlatives below).

The comorbidity of mucositis is an important consideration in this study due to the development of this condition following radiotherapy and as a side effect from chronic use of everolimus. Treatment with everolimus has been designed to begin two weeks after radiotherapy to allow radiation-induced mucositis to start improving. In a pre-clinical model,

concurrent rapamycin treatment with radiotherapy (6Gy/day X 5 days) prevents mucositis due in part to increased expression of mitochondrial superoxide dismutase (MnSOD) (Iglesias-Bartolome 2012). Given the short duration of treatment in this trial (5 days), a delay in the start of everolimus until two weeks after radiotherapy and evidence from this pre-clinical study, we postulate that mucositis will not be a major concern. Patients will be closely monitored for worsening mucositis response once treated with everolimus and if mucositis worsens in 2 out of the first 6 patients, then everolimus 50% dose reduction will be implemented.

5 Population

Patients with locally advanced squamous cell carcinoma of the head and neck, treated with curative intent either in the post-operative or definitive setting with high dose radiotherapy (≥ 50 Gy) with or without chemotherapy will be eligible. Patients will be stratified for exploratory analyses in the analysis phase on the basis of ipsilateral vs bilateral neck irradiation. There will be one treatment group with each patient serving as their own control.

This study will evaluate the response in 10 – 16 patients enrolled at both facilities: St. Joseph's Hospital and Medical Center in Phoenix and Banner – University Medical Center in Tucson (details and justification of sample size in statistical methods) to determine if the proposed everolimus dosing schedule of 5 days is sufficient to show recovery of salivary gland function to pre-treatment levels.

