6.2.2.6 Management of stomatitis / oral mucositis / mouth ulcers

Adverse Drug Reaction	Severity	Afinitor Dose Adjustment and Management Recommendations
Stomatitis	Grade 1 (Minimal symptoms, normal diet)	No dose adjustment required. Manage with non-alcoholic or salt water (0.9%) mouth wash several times a day.
	Grade 2 (Symptomatic but can eat and swallow modified diet)	Temporary dose interruption until recovery to grade ≤ 1 . Re-initiate Afinitor at the same dose. If stomatitis recurs at grade 2, discontinue Afinitor. Manage with topical analgesic mouth treatments (e.g. benzocaine, butyl aminobenzoate, tetracaine hydrochloride, menthol or phenol) with or without topical corticosteroids (i.e. triamcinolone oral paste)*.
	Grade 3 (Symptomatic and unable to adequately eat or hydrate orally)	Discontinue Everolimus
	Grade 4 (Symptoms associated with life-threatening consequences)	Discontinue Afinitor and treat with appropriate medical therapy.

* using agents containing alcohol, hydrogen peroxide, iodine, and thyme derivatives in management of stomatitis as they may worsen mouth ulcers.

Patients with a clinical history of stomatitis/mucositis/mouth ulcers and those with gastrointestinal morbidity associated with mouth/dental infections, irritation of esophageal mucosa e.g. gastroesophageal reflux disease (GERD) and pre-existing stomatitis/mucositis must be monitored even more closely. Patients should be instructed to report the first onset of buccal mucosa irritation/reddening to their study physician immediately.

Stomatitis/oral mucositis/mouth ulcers due to Everolimus should be treated using local supportive care. Please note that investigators in earlier trials have described the oral toxicities associated with Everolimus as mouth ulcers, rather than mucositis or stomatitis. If your examination reveals mouth ulcers rather than a more general inflammation of the mouth, please classify the adverse event as such. The suggested paradigm for treatment of stomatitis/oral mucositis/mouth ulcers is as follows:

1. For mild toxicity (grade 1), no dose adjustment required. Manage with non-alcoholic mouth wash or salt water (0.9%) mouth wash several times a day until resolution.

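### Minor: for a first, intolerable grade 2 oral mucositis, Table 6-1 stops everolimus but the grade 2 row of section 6.2.2.6 interrupts it and restarts it at the same dose

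*Protocol*

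**What the plan says.** Section 6.2.1.2 contains Table 6-1, whose title, "Table 6-1 Dosing guidelines for Everolimus-related non-hematologic toxicities", limits it to reactions attributed to the drug. One of its rows begins "Intolerable grade 2 mucositis, or grade 3 AE", and the action given is to discontinue everolimus. The row does not separate a first episode from a recurrence. The Glossary defines study treatment discontinuation as the "Point/time when patient permanently stops taking study treatment for any reason".

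Section 6.2.2.6 treats stomatitis, oral mucositis and mouth ulcers together and has its own table by grade. Grade 2 has a single row, defined as "Symptomatic but can eat and swallow modified diet". Its action is to interrupt until the event is grade 1 or less, and then: "Re-initiate Afinitor at the same dose. If stomatitis recurs at grade 2, discontinue Afinitor".

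The text leading into Table 6-1 adds a general statement: "Clinical judgment of the treating physician should guide the management plan of each patient based on individual benefit/risk assessment". The same lead-in says that severe or intolerable reactions may call for a temporary hold.

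**The concern.** Whether a grade 2 event is intolerable and whether the patient can still eat a modified diet are separate questions. A patient can be at grade 2 by the definition in 6.2.2.6 and also find the event intolerable. On a first episode, that patient meets the trigger in Table 6-1 (stop) and the trigger in 6.2.2.6 (hold, then resume at the same dose).

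A physician who turns to the dedicated mucositis section and follows its grade 2 row would re-expose the patient after an event that Table 6-1 says should end treatment. Two sites enrol patients, so the same event could be managed differently at each.

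The protocol itself treats mucositis as a toxicity to watch. Everolimus starts two weeks after radiotherapy, when radiation mucositis is expected to be improving but not necessarily gone, and section 4.1 states: "Patients will be closely monitored for worsening mucositis response once treated with everolimus".

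**Working it through.** No formula applies. The check compares the two instructions case by case for everolimus-related oral mucositis.

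| Situation | Table 6-1 (section 6.2.1.2) | Section 6.2.2.6 | Result |
|---|---|---|---|
| Grade 1 | silent | no adjustment | compatible |
| Grade 2, first, tolerable | silent | interrupt, restart at same dose | one instruction |
| Grade 2, first, intolerable | discontinue | interrupt, restart at same dose | **conflict** |
| Grade 2, recurrent | discontinue if intolerable, otherwise silent | discontinue | compatible |
| Grade 3 | discontinue | discontinue | agree |
| Grade 4 | discontinue | discontinue | agree |

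Conflicts: 1 of 6.

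Three further points decide whether that cell is a real conflict.

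1. *Same event?* Yes. The heading of 6.2.2.6 names oral mucositis, and its grade 2 row has no split by tolerability. The numbered advice below that table does not split grade 2 by tolerability either.
2. *Different actions?* Yes. The Glossary makes discontinuation permanent. The grade 2 row of 6.2.2.6 also separates the two actions itself: a temporary hold first, discontinuation only on recurrence.
3. *A rule of precedence?* None for mucositis. The only precedence note under Table 6-1 concerns hepatitis C flare. The clinical-judgment sentence does not rank the two entries, and the remark about holding treatment for intolerable reactions leans away from the row in the table that follows it.

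The effect on the design is nil. Sections 4.1, 6.1 and 9.1 define a dose-limiting toxicity as an everolimus-related event of grade 3 or higher. A grade 2 event is not counted under either entry, so the escalation decision and the total of 10 to 16 patients do not depend on which entry is followed.

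**The case against.** The strongest reply is that this is an ordinary general rule with a specific exception. Table 6-1 picks out intolerable grade 2 while 6.2.2.6 gives the default for grade 2, and the qualifier in Table 6-1 would do no work if the default controlled. On that reading tolerable events are held, intolerable ones are stopped, and only a cross-reference is missing. Both entries are also worded as guidance, and the physician's judgment already decides whether an event is intolerable. Nor is discontinuation used strictly throughout: the grade 3 row of the pneumonitis table (Table 6-3) tells the physician to discontinue until symptoms improve. Finally, the situation may never arise. It needs a drug-related, intolerable, first grade 2 event within a five-day course, with recovery while doses remain to be resumed.

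Much of this stands. The nested reading is the likely intent, and the practical reach is small. What does not stand is that the document settles the matter. Either entry can claim to be the more specific: one carries the qualifier, the other sits in the section devoted to this toxicity. Judgment about tolerability decides whether the Table 6-1 trigger is met, but once it is met the 6.2.2.6 row still applies as written. The loose wording in the pneumonitis table does not carry over, because the stomatitis row itself contrasts a hold with discontinuation.

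**Conclusion.** The inconsistency holds as a minor one. For a first, intolerable, everolimus-related grade 2 oral mucositis the protocol gives two incompatible instructions and no rule for choosing between them. It touches one of the six situations compared. That is a count of cases in the table, not a measure of risk; the protocol gives no rate for this event in a five-day course and none is assumed. The consequence is limited to how many of five doses such a patient receives and whether the patient is re-exposed. No dose-limiting toxicity count, sample size or other stated figure changes.

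The conclusion rests on two readings: that discontinuation in Table 6-1 is permanent, as the Glossary defines it, and that the grade 2 row of 6.2.2.6 covers every grade 2 event meeting its definition.

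**What to change.** In section 6.2.2.6, restrict the grade 2 row to tolerable grade 2 events and add a line stating that intolerable grade 2 leads to discontinuation as in Table 6-1. This writes down the probable intent and adopts the more cautious of the two existing actions.

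The cost is an edit to one table row, with no extra patients, visits, procedures or data. The one downside is that a patient who would have been restarted under the present 6.2.2.6 row may receive fewer than five doses.
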